9.3 VARIABLES

The following data will be collected from medical records and will be recorded in the electronic case report form (eCRF) by investigators (or designees) during the study period:

- Informed consent (where applicable)
- Demographics: age at start of first-line treatment, gender, ethnicity
- Stage of disease (IIIb or IV) at start of first-line treatment
- Type of mutations at initial diagnosis
- Methodology used for mutation testing
- Sites of metastases at start of treatment
- Body weight and height at start of treatment
- Eastern Cooperative Oncology Group (ECOG) performance score (PS) (if available) at start of treatment
- Date of start and end of first-line treatment
- First-line treatment administered
- Starting dose of EGFR-TKI (first-or second-line)
- Dose modification(s) and date(s) of EGFR-TKI
- ECOG PS (if available) at start of second-line treatment
- Type of mutations at start of second-line treatment
- Methodology (allele-specific, NGS, sequencing) and material (tissue/liquid biopsy) used for mutational testing
- Sites of metastases at start of second-line treatment
- Date of start and end of second-line treatment
- Second-line treatment administered

- Reason for discontinuation of each treatment (e.g. progressive disease (PD), adverse event (AE))
- Best response to first and second-line treatment (as documented)
- Date of death
- Bevacizumab use with TKI (Yes/No)

9.3.1 Exposures

Afatinib (Gi(l)otrif®):

Patients were treated with afatinib (Gi(l)otrif®) 50mg or 40mg or 30mg or 20mg tablet once daily as indicated in the approved labels of afatinib (Gi(l)otrif®).

Erlotinib (Tarceva®):

Patients were treated with erlotinib (Tarceva®) 25mg or 100mg or 150mg tablet once daily as indicated in the approved labels of erlotinib (Tarceva®).

Gefitinib (IRESSA®):

Patients were treated with gefitinib (IRESSA®): 250mg tablet once daily as indicated in the approved labels of gefitinib (IRESSA®):

Osimertinib (Tagrisso®):

Patients were/are treated with osimertinib 80 mg or 40 mg tablets once daily as indicated in the approved labels of osimertinib.

The Summaries of Product Characteristics on afatinib, erlotinib, gefitinib and osimertinib are contained in the ISF.

[figure not shown]
9.3.2 Outcomes

9.3.2.1 Primary outcomes

Time on treatment with Epidermal Growth Factor Receptor Tyrosine Kinase Inhibitor (EGFR-TKI). This will be assessed as the time from start of EGFR-TKI treatment until the end of treatment or death date by any cause. In the sequencing cohort it will be assessed as the time from start of afatinib (Gi(l)otrif®) as first-line treatment until the end of the second-line treatment (the last dose of osimertinib) or death date by any cause.

Secondary outcomes

Overall response rate, overall survival, time on treatment until failure of second-line (TTF2, uncommon mutation cohort only), and subsequent therapies used. Methodology and material used for mutational testing.

9.3.3 Covariates

NA

9.4 DATA SOURCES

Data will be collected from patients' medical records and recorded in eCRFs or will be captured from electronic health records (EHR).

9.4.1 Source documents

Source documents provide evidence for the existence of the patient and substantiate the integrity of the data collected. Source documents are filed at the investigator's site. Data entered in the eCRFs that are transcribed from source documents must be consistent with the source documents or the discrepancies must be explained. The investigator may need to request previous medical records or transfer records, current medical records must be available.

For eCRFs all data must be derived from source documents.

9.4.2 Records

Case Report Forms (CRFs) for individual patients will be provided by the sponsor or appointed CRO via remote data capture (RDC) system or Electronic Data Capture (EDC) system.

9.4.3 Direct access to source data and documents

The investigator / institution will permit study-related monitoring, audits, Institutional Review Board (IRB) / Independent Ethics Committee (IEC) review and regulatory inspection, providing direct access to all related source data / documents. eCRFs and all source documents, including progress notes and copies of laboratory and medical test results must be available at all times for review by the sponsor's clinical study monitor, auditor and inspection by health authorities (e.g. FDA). The CRA/on site monitor and auditor may review all eCRFs, and written informed consents (if applicable). The accuracy of the data will be verified by reviewing the documents described in [Section 9.4.1](#).

9.4.4 Storage of records

Study site (s):

The study site(s) must retain the source documents and essential documents (including ISF) according to contract or the local requirements valid at the time of the end of the study (whatever is longer).

Sponsor:

The sponsor must retain the essential documents according to the sponsor's SOPs.

9.5 STUDY SIZE

Uncommon mutation cohort:

In LUX-Lung trials (1200.22, 1200.32, 1200.34), EAP (1200.45, 1200.55, 1200.66, 1200.193) and NIS (1200.205), 267 TKI-naïve patients were treated for uncommon mutations.

- 46% had one of the more frequent afatinib-sensitive uncommon mutation (G719X, L861Q, or S768I),
- 29% had an insertion in exon 20,
- 12% had a de novo T790M,
- 13% had a complex or compound mutation, and
- 10% had other uncommon mutations.

For the current study, a sample size of about 250 is mainly driven by feasibility. We expect that this will result in approximately

- 110 patients with frequent uncommon mutations,
- 70 patients with exon20 insertions, and
- 35 patients with compound mutations.

Given the label (and availability) for first and third generation TKIs, we assume that the majority of patients with these uncommon mutations will have been treated with afatinib. At least 50% of enrolled patients must have been treated with afatinib. At least 50% must have been treated with an EGFR-TKI in first-line (see rationale).

Comparison of the different TKIs will be limited to descriptive statistics because of the limited numbers of patients expected to have been treated with TKI other than afatinib.

Sequencing cohort:

Based on previous data from the GioTag study and expecting a higher proportion of Asian patients, the median time on treatment from start of the first-line treatment until the end of the second-line treatment is projected to be 30 months.

Table 9.5:1 shows the expected (50th percentile) width of the 95% confidence interval to be 13.7 months, with an 80% chance of observing a confidence interval of less than 16.2 months. This is based upon 200 patients with 10 percent random censoring. The width of the confidence interval would increase if the rate of censoring were higher.

Table 9.5:1 95% confidence interval width for median duration of treatment with 200 patients, 30 month underlying median duration, and increasing random censoring¹

95% CI width

	10% censoring	20% censoring	30% censoring
50 th percentile	13.7 months	15.9 months	18.8 months
80 th percentile	16.2 months	18.9 months	22.5 months

¹Calculated by simulation with 10,000 iterations

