9.7 DATA ANALYSIS

The two cohorts will be analysed separately

- Uncommon mutations
- Sequencing of osimertinib after afatinib

The primary endpoint for both cohorts is time on treatment. Kaplan-Meier estimates will be calculated. In addition, the median will be tabulated along with the two-sided 95% confidence interval, using Greenwood's variance estimate.

The following additional endpoints will be analyzed similarly to the primary endpoint.

- overall survival
- time on treatment until failure of second-line (uncommon cohort only)

Patients who were not known to have discontinued treatment will be censored on the date they were last verified to have been on treatment.

A second round of data collection for additional follow-up may be performed in case a substantial proportion of patients had not discontinued treatment before the estimated median time on treatment at the time of the primary data collection.

Best overall response will be tabulated, as will the following:

- demographics
- disease characteristics
- methodology and material used for mutation classification
- anti-cancer drugs used prior to, or after EGFR-TKI (uncommon cohort only).

These endpoints will be analyzed descriptively.

Within the sequencing cohort, the proportion of patients with different types of resistance mutations observed at the time of discontinuation of osimertinib will be categorized and tabulated.

In this study, data will be gathered retrospectively from patients treated within the conditions of the approved marketing authorization of afatinib. Drug exposure during pregnancy, ADRs with causality to Gilotrif (serious or non-serious) and all fatal AEs will be reported to PV on the NIS AE form - excluding deaths to PD of the underlying malignancy. Safety data will be reviewed and analysed as part routine global pharmacovigilance procedures. All adverse events/reactions collected for the study per protocol will be summarised in the final study report.

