4.2.5 Time on treatment

Table 20-SEQ. Time on treatment (ELIGIBLE PATIENTS of the Sequencing Cohort) – Primary objective

The table will provide the Kaplan-Meier estimates of quartiles of time on treatment with the pattern afatinib-osimertinib (with their 95% Confidence Intervals, using Greenwood's variance estimate) (see "Computed variables" chapter). Moreover, a Kaplan-Meier survival curve will be provided. The analysis will be represented on a plot having the time to event on the horizontal axis and the percentage of event-free patients on the vertical axis.

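### The three columns of Table 9.5:1 do not fit one 30-month median; under exponential assumptions the printed interval widths are about 10% to 45% too large, a conservative error

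*Protocol*

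**What the plan says.** Protocol section 9.5 (Sequencing cohort) sets one projected median: "the median time on treatment from start of the first-line treatment until the end of the second-line treatment is projected to be 30 months". The title of Table 9.5:1 applies it to every column: "95% confidence interval width for median duration of treatment with 200 patients, 30 month underlying median duration, and increasing random censoring".

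The printed widths, from a simulation of 10,000 iterations, are:

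| | 10% censoring | 20% | 30% |
|---|---|---|---|
| 50th percentile (months) | 13.7 | 15.9 | 18.8 |
| 80th percentile (months) | 16.2 | 18.9 | 22.5 |

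The text repeats the 10% column as the headline, giving "the expected (50th percentile) width of the 95% confidence interval to be 13.7 months" and adding "with an 80% chance of observing a confidence interval of less than 16.2 months" and "This is based upon 200 patients with 10 percent random censoring".

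The protocol does not give the event distribution, the way censoring was generated, or the scale on which the interval was computed. On the analysis side, section 9.7 says that "the median will be tabulated along with the two-sided 95% confidence interval" and names Greenwood's variance. SAP section 4.2.5 does the same for the "Kaplan-Meier estimates of quartiles of time on treatment with the pattern afatinib-osimertinib". Neither names a transform.

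**The concern.** With the event median held at 30 months, moderate independent censoring should widen the interval only a little, because most patients still contribute information up to the median. The printed widths grow by 18.8/13.7 = 1.37 between 10% and 30% censoring, which is far steeper. The first column is also high. Without censoring, the large-sample width for exponential times is 2 × 1.96 × 30/(ln 2 × √200) = 12.0 months, and 10% censoring should not take that to 13.7.

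These are the only precision figures in the protocol or SAP, and they support the primary estimate of the sequencing cohort. At the tabulated censoring rates they understate the precision to be expected at a 30-month median. They also give a misleading picture of what incomplete follow-up costs.

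**Working it through.** **Inputs.** From section 9.5: n = 200, event median 30 months, censoring 10/20/30%. From section 9.7: Kaplan-Meier median, two-sided 95% interval, Greenwood variance. The rest is unstated, so it was varied.

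**Interval.** The confidence set is all t with |g(S(t)) − g(0.5)| ≤ 1.96 × se{g(S(t))}, where S is the Kaplan-Meier estimate, the standard error comes from Greenwood's variance, and g is the identity (linear), log or log-log. The width is the upper limit minus the lower limit.

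**Step 1: the plan's figures from its stated inputs.** Exponential times (hazard ln 2/30), independent exponential censoring, 10,000 replicates, Monte Carlo error 0.03-0.05 months. Cells are 50th/80th percentile widths in months.

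| | 10% | 20% | 30% |
|---|---|---|---|
| Linear | 12.16/14.31 | 12.42/14.82 | 12.94/15.47 |
| Log | 12.48/14.64 | 12.80/15.21 | 13.42/15.98 |
| Log-log | 12.24/14.39 | 12.51/14.94 | 13.06/15.56 |
| Printed | 13.7/16.2 | 15.9/18.9 | 18.8/22.5 |

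The table is not reproduced. Printed over recomputed at the 50th percentile:
- 10%: 13.7/12.48 = 1.10 to 13.7/12.16 = 1.13
- 20%: 15.9/12.80 = 1.24 to 15.9/12.42 = 1.28
- 30%: 18.8/13.42 = 1.40 to 18.8/12.94 = 1.45

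A separate run with 20,000 replicates gave 12.1-12.4, 12.4-12.8 and 12.9-13.3 months.

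**Step 2: other censoring patterns, median still 30, exponential times.**
- Uniform censoring, log: 12.34/14.56, 12.67/15.05, 13.10/15.56.
- Censoring at month 5, log: 12.78/14.99, 13.60/16.11, 14.68/17.57.
- Censoring at time zero, all transforms, 50th percentile: 12.5-12.8, 13.2-13.6, 14.1-14.5.

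Growth from 10% to 30% is about 1.06-1.08 with independent exponential censoring, 1.13-1.14 with time-zero censoring (compare √(0.9/0.7) = 1.13) and 14.68/12.78 = 1.15 with month-5 censoring. The printed growth is 1.37.

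**Step 3: other event distributions, median still 30.** Weibull with exponential censoring, log interval:
- shape 0.9: 13.74/16.21, 14.10/16.81, 14.81/17.87 (fits the 10% column only)
- shape 0.8: 15.48/18.42, 15.90/19.04, 16.46/20.01 (fits the 20% column only)
- shape 0.7: 17.68/21.16, 18.18/21.89, 18.81/22.99 (close to the 30% column only)

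Lognormal times (sigma 0.6-1.1, log) give 50th-percentile widths of 6.5-11.9 at 10% and 7.1-12.8 at 30%. A hazard falling to 0.2 of its value after month 37, with early censoring (log-log), gives 13.58/25.25, 14.80/29.04 and 16.68/33.34; its 80th percentiles are far above those printed. Each column would need its own distribution.

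**Step 4: a mechanism that fits.** Suppose a random fraction c of simulated event times is flagged as censored at its own time. The event hazard becomes (1 − c) × ln 2/30, so the event median becomes 30/(1 − c): 33.3, 37.5 and 42.9 months. Widths then stretch by 1/(1 − c). Undoing the stretch:
- 50th percentile: 13.7 × 0.9 = 12.3; 15.9 × 0.8 = 12.7; 18.8 × 0.7 = 13.2
- 80th percentile: 16.2 × 0.9 = 14.6; 18.9 × 0.8 = 15.1; 22.5 × 0.7 = 15.8

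All six fall inside the step 1 ranges. The growth also decomposes: the stretch alone gives 0.9/0.7 = 1.286, and 1.372/1.286 = 1.07 is the growth found in step 1. Simulating this mechanism directly gives 13.70/16.19, 15.96/18.97, 19.06/22.83 (log) and 13.46/15.94, 15.62/18.55, 18.61/22.20 (log-log), all within about 2% of print.

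**The case against.** **The search is finite.** The protocol states no distribution, censoring mechanism or transform, and Greenwood's variance is named for the analysis rather than for this simulation. Strictly, what is shown is that no model tried reproduces the table. The headline pair, 13.7 and 16.2 months, could be right on its own under a Weibull shape near 0.9. Both points stand. They do not rescue the table, because its caption holds the median fixed across columns and the printed growth is out of reach of every fixed-median model tried that also keeps the 80th percentiles in range.

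**The cause is a fit.** No single transform matches all six cells within simulation error; gaps of 0.2-0.3 months remain. That is fair. Confidence attaches to the failure to reproduce the table, not to the explanation.

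**It may be a labelling matter.** If 30 months were the median of recorded durations, censored or not, the widths would be roughly right and the caption wrong. This sits badly with a projected, underlying median, and the columns would then describe three different event medians. The table would still need correcting.

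**Little depends on it.** No target width is set, the sample size is not derived from one, and the SAP describes the objectives as descriptive. This is correct and limits the importance of the point.

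**Real censoring may exceed 30%.** Section 7.2 reports 52% maturity for time to treatment failure in the earlier study. If censoring here were 48% (an assumption; the protocol expects better maturity and allows a second data collection), the same exponential model gives about 14.4-15.2 months, 80th percentile 17.8-19.1. A corrected 10% figure quoted alone could therefore look optimistic. This stands and bears on the fix.

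**Conclusion.** The concern holds. Table 9.5:1 does not follow from one 30-month event median. Under exponential times and independent exponential censoring, across linear, log and log-log intervals, the printed 50th-percentile widths are too large by about 10-13%, 24-28% and 40-45%, and the 80th percentiles by similar proportions. The percentages depend on those assumptions. The inconsistency between columns does not depend on the exponential shape: it persists under every distribution tried.

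The table also exaggerates the cost of censoring: +37% in width from 10% to 30%, against about +6-8% with independent exponential censoring and about +14-15% with dropout at month 5.

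The error is conservative at the tabulated censoring rates. It does not call the 200 patients into question and changes nothing in conduct. Flagging event times as censored is the likely cause, but it is an inference.

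**What to change.** Rerun the simulation with event and censoring times drawn separately, so that the event median stays at 30 months in every column. Beside the table, state the event distribution, the censoring mechanism and the interval transform, using the transform intended for the analysis.

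Replace the table and the sentence that quotes 13.7 and 16.2 months. Under exponential assumptions the new 10% figures would be about 12.2-12.5 and 14.3-14.6 months; the final values depend on the choices stated. A further column at heavier censoring would keep the corrected headline from reading as optimistic.

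The cost is one simulation rerun, one table and one sentence in the protocol, with no change to sample size or conduct.

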In addition, osimertinib has been studied in the first-line treatment in the FLAURA trial. Osimertinib significantly prolonged PFS compared to first generation TKIs (erlotinib or gefitinib). Median PFS by independent review was 17.7 months in patients with common mutations ([R18-0130](#)). Overall survival data are still immature and so far, only 29% of the patients treated first-line with osimertinib received a subsequent therapy. Furthermore, as more than 60% have no putative resistance mechanism and even those identified are not druggable with approved targeted therapies, the best sequencing strategy is still under discussion.

A recent global real-world study (GioTag) recruited from December 2017 to May 2018 and provided insights into the outcomes of patients treated with the sequence afatinib followed by osimertinib. Time on treatment for the sequence was 27.6 months and 2 year survival rate being 79% ([P18-09968](#)). This study enrolled mainly Caucasian patients (59%) and 63% of the patients came from USA, although incidence of EGFR mutated NSCLC is much higher in Asian countries ([R19-1657](#)). Study timelines and availability of drugs led to limited enrolment of long-term responders (10-12% of patients treated with afatinib are for 3 years and longer on drug) ([P19-03124](#)) and maturity of time to treatment failure was 52% and 31% for OS. Thus, more data from Asian patients and with meanwhile longer availability of both drugs will provide data that are more robust with an increased maturity. At least 60% of enrolled patients should have Asian ethnicity.

Various methodologies with different sensitivities can be used for T790M detection. Recently, it could be shown that in patients who progressed under treatment with an EGFR TKI, the T790M positivity rate was 66% using ddPCR, but only 24% using Cobas ([P19-03686](#)). Thus, it is of interest to learn more about the methods that have been used to identify patients qualifying for the sequence afatinib followed by osimertinib.

Investigating in this real-world data (RWD) study the time from start of first-line afatinib (Gi(l)otrif®) until the end of second-line osimertinib in this study provides insights on treatment sequence that can inform on the most beneficial treatment sequence for the patients.

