Sequencing cohort: Patients treated with afatinib (Gi(l)otrif®) and/or osimertinib in interventional trials are excluded to ensure the non-interventional setting of this study. Real-world studies such as ASTRIS are not affected by this exclusion ([R17-0754](#)). The threshold of start of osimertinib at least 10 months prior to data entry was chosen based on the median PFS result of AURA-3 ([P17-01960](#)) to avoid early censoring and enable collection of mature data on treatment duration. All patients fulfilling inclusion and exclusion criteria from a site will be entered to avoid bias.

A log of all patients included into the study will be maintained in the ISF at the investigational site.

BI reserves the right to discontinue the study overall or at a particular study site at any time for the following reasons:

1. Failure to meet expected enrolment goals overall or at a particular study site.
2. Violation of Good Clinical Practice (GCP) (as applicable), the Study Protocol, or the contract by a study site or investigator, disturbing the appropriate conduct of the study.

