9.9 LIMITATIONS OF THE RESEARCH METHODS

Potential limitations of the study design:

1. Site selection:

In general, having a clearer focus on Asian countries reflects the higher incidence of EGFR mutations in this group.

1. a) Uncommon mutation cohort: There are no limitations coming from the site selection.

1. b) Sequencing cohort: The study is restricted to the sites using afatinib (Gi(l)otrif®) on a regular basis and to the sites which are able to use osimertinib for T790M mutation tumours. By the time of data collection, osimertinib has been approved (and reimbursed) in most regions not longer than 2 to 3 years, which limits the number of patients being treated with osimertinib.

To overcome this feasibility limitation, patients who have received osimertinib treatment within an EAP/CUP are eligible as well as patients who started osimertinib treatment at least 10 months prior to data entry, increasing the pool of eligible sites and potential patients.

2. Patient population:

2. a) Uncommon mutation cohort: Firstly, there is a bias as only patients that were tested for uncommon mutations and were treated with an EGFR-TKI could be enrolled into this NIS. Because of that bias, the results of the study will not be generalizable to all patients harbouring an uncommon mutation.

This study has no comparator group limiting the interpretability of the results as they cannot be put into perspective. The planned analyses by EGFR-TKI used includes no formal testing for statistical significance.

2. b) Sequencing cohort:

Firstly, there is an immortal time bias as patients that die on afatinib (Gi(l)otrif[®]) will not be included in this study. Because of that immortal time bias, the results of the study (i.e. median duration from start of afatinib (Gi(l)otrif[®]) until the end of osimertinib) will not be generalizable to all patients starting first line treatment with afatinib (Gi(l)otrif[®]).

Secondly, there is still some bias as patients with long-term benefit from afatinib (Gi(l)otrif[®]) have a lower likelihood of being included in this study. Because of bias, the results of the study (i.e. median duration from start of afatinib (Gi(l)otrif[®]) until the end of osimertinib) will not be generalizable to all patients starting first-line treatment with afatinib (Gi(l)otrif[®]).

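### The 13.7-month precision for the sequencing cohort rests on an unexplained 10% censoring rate and on a table that does not keep its stated 30-month median

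*Protocol*

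**What the plan says.** Protocol 9.5 gives the sequencing cohort no hypothesis test. Its size of 200 is supported by a precision statement alone. The median time from afatinib start to the end of "second-line treatment is projected to be 30 months". Table 9.5:1 then "shows the expected (50th percentile) width of the 95% confidence interval to be 13.7 months". The text puts the probability of an interval narrower than 16.2 months at 80%. The condition follows at once: "This is based upon 200 patients with 10 percent random censoring". The table is headed as having a "30 month underlying median duration, and increasing random censoring", with columns for 10%, 20% and 30%. The 50th percentiles are 13.7, 15.9 and 18.8 months, and the 80th percentiles 16.2, 18.9 and 22.5. The text says that the interval widens with more censoring. It does not say why 10% is the planning case, which event-time distribution was used, or how censoring was generated.

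Three other places bear on the rate:
- Protocol 7.2, on the predecessor real-world study: "maturity of time to treatment failure was 52% and 31% for OS".
- Protocol 9.2.1: "The threshold of start of osimertinib at least 10 months prior to data entry was chosen based on the median PFS result of AURA-3".
- Protocol 9.9: by the time of data collection, "osimertinib has been approved (and reimbursed) in most regions not longer than 2 to 3 years".

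**The concern.** The quoted precision uses the most favourable of three columns. If maturity means the share of patients with an event, the predecessor had about 48% censored (100 − 52), beyond the table's last column. The entry threshold is tied to a median PFS. If time on osimertinib resembles that PFS, about half of the patients entered at the threshold are still on drug. SAP chapter 3 adds further censoring: living or untraceable patients whose discontinuation status is unknown are censored at their last dose-record start date.

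This paragraph is the only quantitative support for 200 patients. If neither the censoring rate nor the simulation behind it matches the design, the reader has no usable statement of how precisely the primary median will be estimated.

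**Working it through.** **1. Reproduce the plan's figures.** Assume exponential times, n = 200, median 30 and Kaplan-Meier limits with Greenwood variance. With independent exponential censoring of a share p, the approximate width is

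W(p) = 2 × 1.96 × (30/ln 2)/√200 × √[(1−p)(2^(1/(1−p)) − 1)] = 12.0 × √[(1−p)(2^(1/(1−p)) − 1)].

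At p = 0.10 the root is √(0.9 × 1.160) = 1.022, so W is 12.3. Simulation gives the widths below in months (50th / 80th percentile, log-log limits).

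| Censored | Table 9.5:1 | Independent censoring, true median 30 | Events relabelled as censored | Estimated median when relabelled |
|---|---|---|---|---|
| 10% | 13.7 / 16.2 | 12.2 / 14.2 | 13.5 / 15.9 | 33.3 |
| 20% | 15.9 / 18.9 | 12.5 / 14.8 | 15.6 / 18.5 | 37.6 |
| 30% | 18.8 / 22.5 | 13.0 / 15.5 | 18.5 / 22.2 | 42.8 |

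Two other mechanisms also miss the plan's 50th percentiles. Independent uniform censoring gives 12.1, 12.4 and 12.8. Censoring a random share of patients at a uniform fraction of their own time gives 13.0, 14.2 and 16.0.

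The relabelling mechanism draws times with a 30-month median and marks a random share p of them as censored at those same times. It matches all six cells within 3%. It also cuts the event hazard by the factor (1−p), so the median being estimated is 30/(1−p): 33.3, 37.5 and 42.9 months. The plan's 50th percentile rises 37% from the 10% to the 30% column (18.8/13.7 = 1.37). Independent censoring gives a rise of about 6% (13.0/12.2). Most of the table's increase therefore comes from a moving median.

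**2. Censoring implied by the follow-up.** Assume exponential time on osimertinib with median m, and follow-up uniform from 10 to T months after osimertinib start. The share still on drug is

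(m/ln 2) × (2^(−10/m) − 2^(−T/m))/(T − 10).

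Two values of m are used. The low case, 10, is inferred from the entry threshold. The high case is 30 − 13.7 = 16.3, where 13.7 is the LUX-Lung 7 time to treatment failure in Protocol 7.2; subtracting medians is only approximate. T is 24 to 36 from the 2-to-3-year statement. More generously, T is 49 or 61, counting from the first US approval (November 2015) to December 2019 or the end of 2020.

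| m | T = 24 | T = 36 | T = 49 | T = 61 |
|---|---|---|---|---|
| 10 | 32% | 23% | 17% | 14% |
| 16.3 | 49% | 39% | 32% | 27% |

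If every patient sat at the 10-month floor, the share would be 50% (m = 10) or 65% (m = 16.3). Reaching 10% needs uniform follow-up out to about 82 or 163 months, or a fixed 33 or 54 months for every patient.

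**3. Width at 23% to 49% censoring.** With a true 30-month median and independent exponential censoring, the formula gives 12.7 to 14.6 and simulation 12.7 to 14.8, so about 12.7 to 14.7. The simulated 80th percentile is 14.9 to 18.3. Uniform censoring gives 12.5 to 14.1 (80th: 14.8 to 17.3). At 40% the formula gives exactly 13.7.

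**4. Two-stage simulation of the design.** Exponential afatinib time plus exponential osimertinib time, overall median 30, follow-up from osimertinib start as in step 2:

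| m, T | Censored | Width, 50th / 80th |
|---|---|---|
| 10, 49 | 17% | 8.8 / 10.2 |
| 10, 36 | 23% | 9.2 / 10.9 |
| 10, 24 | 32% | 10.8 / 13.0 |
| 16.3, 36 | 39% | 9.6 / 11.6 |
| 16.3, 24 | 49% | 12.0 / 15.3 |

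The intervals are narrower because the sum of two stages is less dispersed than a single exponential. The estimated medians were 30.6 to 32.3, so this follow-up pattern also pushes the Kaplan-Meier median slightly upwards.

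**The case against.** The plan is open about its condition: 10% is stated, the direction of the effect is stated, and 20% and 30% are tabulated. Protocol 7.2 expects greater maturity than in the predecessor because both drugs have been available longer. Early-access, compassionate-use and deceased patients may be enrolled, which lengthens follow-up or adds events. Protocol 9.7 allows a second round of data collection. The study is descriptive, so nothing passes or fails on the width.

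All of this stands, and it makes the point an unsupported planning figure, not a concealed one. It does not supply the 10%. None of the mitigations is quantified, and the second round is optional. Under the step 2 model, d further months of follow-up multiply the censored share by 2^(−d/m). Getting from 23.2% to 10% takes 10 × log2(2.32) = 12.1 months, and from 49.3% it takes 16.3 × log2(4.93) = 37.5 months. Only the most generous reading, 13.7%, comes close (10 × log2(1.37) = 4.5 months).

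A reader might go further and infer that the interval will be much wider than stated: 18.8 months from the 30% column, or more by extrapolating to 48%. The documents do not support that. Those columns reflect a median that has drifted to about 43 months at 30% censoring. With the median held at 30, 30% censoring gives about 13.0 months.

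**Conclusion.** Two things hold. First, 10% censoring is unexplained, and no reading tried of the protocol's own follow-up figures reaches it. The range is about 23% to 49% under the step 2 assumptions and about 14% to 65% across all readings. These shares are not stated in the protocol. They rest on exponential durations, uniform follow-up, a 10-month osimertinib median inferred from the threshold, and a subtraction of medians.

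Second, Table 9.5:1 does not agree with its own heading. Among the mechanisms tried, all with exponential times, only relabelling reproduces it, and that estimates medians of about 33, 37 and 43 months instead of 30.

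It does not follow that 13.7 is too narrow. With the median at 30 and independent censoring, 12.7 to 14.7 months brackets it, and an 80th percentile of about 15 to 18 brackets 16.2. The two-stage runs give about 9 to 12. The figure is of plausible size, but it is not derived from this design. Correcting it is worthwhile because the cohort size rests on it. The descriptive purpose and the disclosure limit the consequence.

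**What to change.** In Protocol 9.5, re-run the simulation with a true 30-month median and administrative censoring taken from the design: the 10-month floor after osimertinib start plus the availability window. State the event-time distribution, the censoring mechanism and the confidence interval method. Replace 13.7 and 16.2, and all of Table 9.5:1, with the results. Give the expected censoring rate and its reason, and extend the table to 40% and 50%.

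Do not simply promote the existing 30% column (18.8 and 22.5) or extrapolate it. That would put a less accurate figure in place of the present one.

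The cost is one paragraph and one re-run. No extra patients are needed, and the restated width may turn out larger or smaller than 13.7.
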